### **3.1 Inclusion Criteria**

1. For a subject to be eligible for this study, he or she must meet **all** of the following criteria: Is a male or female subject between the ages of 18 and 65 years, inclusive.
2. Has body mass index (BMI) between >22 and <40.
3. Has SMF bulge that is contiguous and fits to 32±4 injections sites according to a grid with 1 centimeter (cm) distance between injection points.
4. Has grade 3 to 4 of SMF as rated by the C-CAT.
5. Has a visible or large pocket of submental fat- according to physician global assessment.
6. Has grade 3 to 4 of SMF as rated by the S-CAT.
7. Has stable weight, with no fluctuation of >5 kg in the past 12 months.
8. If female, is not pregnant or breastfeeding based on the following:
  - a. agree to the use of highly effective contraceptive methods for at least 2 weeks before baseline until 4 weeks after the last day of study drug and a negative serum pregnancy test ( $\beta$ -hCG) at screening and negative urine pregnancy test at baseline; or
  - b. is of nonchildbearing potential defined as clinically infertile as the result of surgical sterilization (hysterectomy, bilateral tubal ligation, and/or bilateral oophorectomy); or
  - c. is confirmed postmenopausal status (defined as either having amenorrhea for  $\geq$  12 consecutive months without another cause and documented serum follicle-stimulating hormone (FSH) level  $>$  40 mIU/mL or another documented medical condition (e.g., was born without a uterus))

NOTE: The following are considered highly effective contraceptive methods: hormonal oral contraceptives, injectables, and patches; intrauterine devices; double-barrier methods (synthetic condom, diaphragm, or cervical cap used with spermicidal foam, cream, or gel); and male partner sterilization.

9. If male (with or without vasectomy), agree to the use of highly effective contraceptive methods e.g., condom , from study check-in until 7 days after the last day of study drug.
10. Is willing to avoid strenuous exercise for seven (7) days post treatment.
11. Is able to adhere to the visit schedule and protocol requirements and be available to complete the study.
12. Is willing and able to sign an Institutional Review Board (IRB) approved informed consent form (ICF) indicating that they are aware of the investigational nature of the study.

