#### 4.11 Clinician-Chin Assessment Tool (C-CAT)

SMF ratings using the C-CAT will be conducted by the Investigator at screening and baseline and at study visits on Days 28, 56, and 84 to assess the change in SMF severity before and following treatment.

The C-CAT score will be based on the Investigator's clinical evaluation of the subject in the Frankfurt horizontal plane. Clinical evaluation will include palpation of the chin and neck area, anterior, oblique and profile views of the chin and neck, and observation of pronation, supination, and lateral movement of the head. The score will be determined using the rating scale definitions. The score will be recorded as a whole number. At screening, the score will be used in conjunction with inclusion criteria.

The C-CAT is defined below. The scale is A 5-point scale (scored 0-4).

The grading system categorizes 3 aspects of submental chin fat: bulge, (size of the submental fat bulge) neck (extension of the bulge into the neck, downward and lateral) and jawline (the appearance of the jawline, presence of fat and definition of the jawline).

Each grade contains a description and a line drawing. Each grade is distinct and non-overlapping.

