### **12.3 Endpoints Analyses**

All measured variables and derived parameters will be listed individually and, if appropriate, tabulated by descriptive statistics.

For categorical variables, summary tables will be provided giving sample size, absolute and

relative frequency, and 95% confidence interval (CI) for proportions by study arm.

For continuous variables, summary tables will be provided giving sample size, arithmetic mean, standard deviation, coefficient of variations (CV%), median, minimum and maximum, and 95% CI for means of variables by study arm.

The data will be analyzed using the SAS version 9.4 (SAS Institute, Cary North Carolina).

For the primary endpoint analysis, Pearson's chi-square test will test the statistical significance of the difference in the proportion of responding subjects between the high dose RZL-012 group and the placebo group. A responder is defined as a subject who has at least a 1-grade improvement between Day 84 and baseline on the C-CAT.

Secondary endpoints (improvement in 1 point in S-CAT and C-CAT, improvement in 2 points in both S-CAT and C-CAT) will be tested using a two-sided test of equality of binomial proportions at the alpha=0.05 level of significance. If the primary analysis is not statistically significant, then the results of the secondary analysis will be exploratory rather than confirmatory.

All other secondary endpoints will be tested using a two-sided test at the alpha=0.05 level of significance.

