### Secondary Endpoints:

MediStat Statistics in Medicine	DOCUMENT NUMBER: 140-BST-PLN-001	PAGE: 9 of 16
TITLE: Statistical Analysis Plan of Protocol Number RZL-012-SMF-P2bUS-001	EFFECTIVE DATE : 08/03/2022 REVISION NUMBER : 1.0	

- Proportion of subjects who have at least a 1-grade improvement in both the C-CAT and S-CAT (Day 84 versus baseline) in the RZL-012 groups versus placebo group.
- Proportion of subjects who have at least a 2-grade improvement in both the C-CAT and S-CAT (Day 84 versus baseline) in the RZL-012 groups versus placebo group.
- Reduction in SMF volume by MRI (Day 84 versus screening) in the RZL-012 groups versus placebo group.
- Reduction in SMF thickness measured with caliper (Day 84 versus baseline) in the RZL-012 groups versus placebo group. Safety assessment of RZL-012 in the treatment of SMF reduction.
- safety of RZL-012 in the treatment of SMF reduction.

Exploratory endpoints:

- Physicians Global Assessment
- SMF improvement using the Global Aesthetic Improvement Scale (GAIS).
- Subject Global Self-Assessment
- SMF improvement using the Subject Global Assessment of Change Scale.
- SMF improvement using the subject's satisfaction questionnaires.
- SMF improvement using Subject's impact questionnaire.

- Study Design

This is a Phase 2b, double-blind, randomized, three-arm, placebo-controlled study that consists of a screening period, baseline period, and a randomized treatment period. Subjects receive a single treatment session that consists of multiple injections of RZL-012 or placebo into the submental area under the chin, after which they are monitored for safety and efficacy over 84 days.

Following the completion of Day 84 visit of the last subject, subjects from three (3) chosen clinical sites are followed up to a 1 year after injection to evaluate the long term safety and efficacy. The additional follow up visits are conducted at 6 and 12 months after injection.

Study participants are adult volunteers (135 subjects - 45 subjects per group) of 18 to 65 years of age who have consented to participate in this study. Each subject is randomized to either active treatment (high or low dose RZL-012) or placebo at a ratio of 1:1:1 per group and receives one of the following:

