For the primary endpoint (proportion of high dose group subjects who have at least a 1-grade improvement from baseline to Day 84 on the C-CAT scale), the assumed true rates are 70% in the RZL-012 high dose group and 35% in the placebo group (a difference of 35 percentage points). Based on the use of a two-sided test of equality of binomial proportions at the alpha=0.05 level of significance, 41 subjects per group are required at 90% power. In order to account for a dropout rate of up to ~9%, the planned sample size is 45 subjects per group, for a total sample size of 135 subjects.

- **Statistical Analysis Software and Data Management**

Data manipulation, tabulation of descriptive statistics, calculation of inferential statistics, and graphical representations will be performed using SAS® version 9.4 or higher for Windows. If the use of other software is warranted, the final statistical methodology report will detail what software was used for what purposes.

- **Data Management**

Data management for the study is performed by Medistat.

- **Medical Coding**

Concomitant medications entered into the database are coded using the WHO (World Health Organization) Drug Public Website Dictionary named WHOCC-ATC/DDD index, which employs the Anatomical Therapeutic Chemical classification system.

Adverse events are coded using the most updated version of Medical Dictionary for Regulatory Activities (MedDRA) terminology.

Medical history events are coded using the most updated version of Medical Dictionary for Regulatory Activities (MedDRA) terminology.

- **Handling of Missing data**

Every effort will be made to obtain all data from all subjects who have been enrolled, to minimize missing data.

A subject with missing primary endpoint data will be imputed as treatment failure.

- **Subject Population for analyses**

MediStat Statistics in Medicine	DOCUMENT NUMBER: 140-BST-PLN-001	PAGE: 13 of 16
TITLE: Statistical Analysis Plan of Protocol Number RZL-012-SMF-P2bUS-001	EFFECTIVE DATE : 08/03/2022 REVISION NUMBER : 1.0	

The Intent-to-treat population (ITT) will consist of all enrolled subjects who received the study treatment, (exposed population), including subjects prematurely withdrawn. The ITT population will serve as the principal data analysis set for analyses of efficacy and safety endpoints. Subjects will be analyzed according to the treatment received

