The Chi-Square test will be applied to test the statistical difference between the placebo group and the RZL-012 high-dose group in responder rate at Day 84. Responder rate is defined as the percentage of subject achieving at least a 1-grade improvement from baseline in C-CAT.

- **Analysis of secondary Endpoints**

Secondary endpoints (improvement in 1 point in S-CAT and C-CAT, improvement in 2 points in both S-CAT and C-CAT) will be tested using a two-sided test of equality of binomial proportions at the alpha=0.05 level of significance.

All other secondary endpoints will be tested using a two-sided test at the alpha=0.05 level of significance.

- The Chi-Square test will be applied to test the statistical difference between the placebo group and each of the RZL-012 dose groups in the responder rate at Day 84 where responder rate is defined as the percentage of subject achieving at least a 1-grade improvement from baseline in both S-CAT and C-CAT.
- The change and percentage of change from baseline at Day 84 in SMF thickness measured with caliper and in SMF volume by MRI will be calculated along with 95% Confidence intervals.

The Paired T-test for two means (paired observations) will be applied for testing the statistical significance of the change and percentage of change from baseline at Day 84 in SMF thickness measured with caliper and in SMF volume by MRI within each study group.

MediStat Statistics in Medicine	DOCUMENT NUMBER: 140-BST-PLN-001	PAGE: 15 of 16
TITLE: Statistical Analysis Plan of Protocol Number RZL-012-SMF-P2bUS-001	EFFECTIVE DATE : 08/03/2022 REVISION NUMBER : 1.0	

The two-sample T-test for independent samples will be applied for testing the statistical significance of the change and percentage of change from baseline at Day 84 in SMF thickness measured with caliper and in SMF volume by MRI between each of the RZL-012 dose groups and the placebo group.

- Analysis of Exploratory endpoint
  - SMF improvement

The SMF improvement using the Global Aesthetic Improvement Scale (GAIS) , the physician Global Assessment of Change Scale, Subjects Global Self-Assessment of Change Scale, Subject Global Assessment of Change Scale, the subject's satisfaction questionnaires, and the subjects's impact questionnaire will be summarized at each timepoint and by treatment group.

- Analysis of Safety

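### The primary chi-square test is valid but leaves out the baseline C-CAT grade (3 or 4); stratifying by it would give a modest gain in power if grade predicts response

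*SAP*

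**What the plan says.** Protocol 3.1, criterion 4, restricts entry by clinician rating: "Has grade 3 to 4 of SMF as rated by the C-CAT". Protocol 4.11 has the rating made twice before treatment: "SMF ratings using the C-CAT will be conducted by the Investigator at screening and baseline". Protocol 8.2 lists the C-CAT among the Day 0 assessments. A responder is a subject who improves by at least one grade from baseline to Day 84. SAP section 6 defines baseline as the last evaluable value before injection.

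The primary test in SAP section 6 is: "The Chi-Square test will be applied to test the statistical difference between the placebo group and the RZL-012 high-dose group in responder rate". Protocol 12.3 agrees: "Pearson's chi-square test will test the statistical significance of the difference in the proportion of responding subjects". Neither text has a covariate, stratum or model. Protocol 8.3 describes a predefined 1:1:1 scheme across sites and mentions no stratification by grade. The only sensitivity analysis named in the SAP is the per-protocol set. The two responder endpoints that combine C-CAT and S-CAT are also compared as unadjusted proportions.

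The sample size rests on this assumption: "the assumed true rates are 70% in the RZL-012 high dose group and 35% in the placebo group". The SAP concludes: "two-sided test of equality of binomial proportions at the alpha=0.05 level of significance, 41 subjects per group are required at 90% power". It then allows for dropout: "In order to account for a dropout rate of up to ~9%, the planned sample size is 45 subjects per group".

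**The concern.** The same one-grade success is a different hurdle at the two entry grades. By the C-CAT descriptions in protocol 4.11, a subject who moves from 4 to 3 may still have fat in the neck above the laryngeal prominence. A subject who moves from 3 to 2 must have none there. Grade 4 is also the top of the scale, so rating error at that grade can only go downward. It is therefore plausible, though the documents do not show it, that response rates differ by starting grade.

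If they do, the chance difference between arms in the grade mix adds random error to the observed difference in response. Neither the randomisation as described nor the analysis removes it. The cost is some power and precision on the primary comparison, from a variable that is already collected. An adjustment chosen after unblinding would be post hoc.

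**Working it through.** **Inputs.** From the documents: response 70% versus 35%, two-sided alpha 0.05, power 90%, 41 per group required and 45 planned, allocation 1:1:1. Assumed, because the documents are silent: the share at grade 4 (50% unless stated) and the gap in response between the two grades. Overall arm rates are held at 70% and 35%.

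**1. The plan's own figure.** With pooled variance and no continuity correction,

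n = [1.960 × √(2 × 0.525 × 0.475) + 1.282 × √(0.70 × 0.30 + 0.35 × 0.65)]² / 0.35² = 40.7, so 41 per group.

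Normal-theory power is 90.2% at 41 and 92.7% at 45. The stated size is right for the stated test.

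**2. How far chance imbalance can move the result.** At 45 per group and a 50/50 grade mix:

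- SD of the between-arm difference in grade-4 share = √(2 × 0.25 / 45) = 0.105, or 10.5 points.
- The observed difference in response shifts, per SD, by gap × 10.5 points: 1.1 points for a 10-point gap, 2.1 for 20 and 3.2 for 30.
- Standard error of the observed difference = √[(0.70 × 0.30 + 0.35 × 0.65) / 45] = 0.099, or 9.9 points.

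Imbalance therefore accounts for about (1.1/9.9)² = 1%, (2.1/9.9)² = 4.5% and (3.2/9.9)² = 10% of the sampling variance. This is the part that stratification can remove.

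**3. Power at 45 per group.** Simulation with simple randomisation, Pearson chi-square against CMH with two strata, at least 200,000 trials per scenario, 50/50 mix:

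| Response gap between grades | High-dose rates | Placebo rates | Chi-square | CMH | Gain (points) |
|---|---|---|---|---|---|
| 0 | 70 / 70% | 35 / 35% | 92% | 92% | about 0.1 |
| 10 points | 75 / 65% | 40 / 30% | 92% | 92.5% | about 0.5 |
| 20 points | 80 / 60% | 45 / 25% | 92% | 93.5% | about 1.5 |
| 30 points | 85 / 55% | 50 / 20% | 92% | 95% | about 3 |

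A second parameterisation, by odds ratio for response between grades and with 30% to 50% at grade 4, agrees. Gains are 0.7 to 0.9 points at an odds ratio of 2, 1.6 to 1.8 at 3, and 2.8 to 3.2 at 5.

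**4. With missing data.** The SAP counts missing primary data as failure. With 9% missing at 45 per group, chi-square power is 86.0%. CMH power is 86.3%, 87.6% and 89.4% for gaps of 0, 20 and 30 points, so the gains are 0.3, 1.6 and 3.4 points, of the same order as in step 3.

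**5. Power at 41 per group.** With no grade effect, chi-square has 91.5% and CMH 89.9%, a loss of 1.6 points. With a 20-point gap CMH is still about 0.4 points lower. Part of this is discreteness.

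**6. Type I error.** Across the odds-ratio scenarios chi-square rejected in 5.0% to 5.4% of null trials and CMH in 4.9% to 5.0%.

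**The case against.** The strongest reply is that nothing here is wrong. A chi-square test on randomised arms is valid, it is the test the sample size was computed for, and chance imbalance is random error that its type I error already covers. All of that stands. A reader might infer that the primary result would be biased by grade imbalance, or that 41 per group is too few for the stated test. The documents support neither.

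The second reply is that the benefit is unproven, since no text gives the grade split or links grade to response. This stands too, and the gains must be read as conditional. A reader might infer a loss of 5 points or more. That needs an odds ratio near 10, or a gap of about 50 points (95% versus 45% on high dose and 60% versus 10% on placebo between adjacent grades). Nothing in the documents points to a relation that strong. The 86% power in step 4 comes from counting missing data as failure, which is a separate matter from the choice of test.

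The third reply is that stratifying is not always free. At 41 per group with no grade effect it costs 1.6 points. That also stands, but the SAP keeps every treated subject in the primary set, so 45 is the relevant size if all those randomised are treated. At 45 CMH lost no power in any scenario examined.

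**Conclusion.** The point holds as a modest inefficiency. The plan records the baseline C-CAT grade, measures response from it, and uses it neither in the randomisation as described nor in the primary test. At 45 per group, stratifying by grade is worth between nothing and about 3 points of power for response gaps of 0 to 30 points. The case for it is that the data exist, the test is standard, the direction of the grade effect need not be known, and power at the planned size is essentially unchanged if grade does not matter. The size of the gain rests on an assumed grade split and an assumed relation to response.

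**What to change.** Before unblinding, amend SAP section 6 and protocol 12.3 as follows.

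- **Primary test:** Cochran-Mantel-Haenszel test of high dose versus placebo, stratified by baseline C-CAT grade, in the same ITT set, two-sided 0.05.
- **Strata:** the last C-CAT value before injection, grade 4 versus grade 3 or lower. This also places any subject whose Day 0 rating falls below the entry range, a case the documents do not cover.
- **Estimate:** the Mantel-Haenszel stratified risk difference with its 95% confidence interval. Without it, the test would be adjusted and the reported effect would not.
- **Sensitivity analysis:** the Pearson chi-square as now written.
- **C-CAT plus S-CAT responder endpoints (1-grade and 2-grade):** the same CMH test, stratified by baseline C-CAT grade.

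The cost is about one sentence in each document, with no new data, visits or subjects. The statistical downside is a possible loss of up to about 2 points of power if only about 41 per group are analysed and grade is unrelated to response.

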**Figure 6: Diagram of Injection Pattern**

Subjects were injected with RZL-012 or vehicle perpendicularly (90°) to the skin. An ice pack was placed on the injected area for pain relief immediately after injection. Subjects had to remain seated in the injection position for an additional 10 minutes after dosing.

RZL-012-SMF-P2a-US-001 Results:

AEs were closely followed up throughout the study to determine the safety profile of RZL-012. Different scales were used to grade the severity degree of edema and erythema, pain, bruising and induration. Most of AEs were treatment related.

The most commonly reported AEs were bruising, induration, edema, pain and erythema all of which were reported with a similar incidence in the RZL-012 and placebo treatment groups. A difference was evident in the severity of some of the AEs in the RZL-012 high-dose treatment group vs. placebo with 3 reports by 3 subjects of severe edema and 2 reports by 2 subjects of severe induration in the high dose group. However, these AEs were characterized as such only within the first 24 hours of administration. The intensity then went from moderate to mild in the days following the RZL-012 injection and were completely resolved by 56 days after injection without any specific treatment or medication. Erythema, and bruising were not dose related and were mostly resolved at 14 days after injection. There were no clinically significant changes in vital signs, no deaths and no SAEs in any subjects.

Based on the objective MRI, it can be concluded that the efficacy of RZL-012 in reducing SMF in this Phase 2a study was demonstrated. This is evident by both the change in the submental depth (thickness) as well as volume. The robustness of these results is supported by the dose response that shows larger effects for the higher dose of RZL, i.e., a volume reduction of -22.2% $\pm$ 14.9 vs. Volume reduction of -10.6% $\pm$ 14.5 and -0.4% $\pm$ 13.9 for RZL-012 low dose and placebo, respectively.

The objective MRI assessments were supported by the Physician Impression scale. This scale which shows a more pronounced improvement at days 56 and 84 compared to day 28 may indicate that the effects of RZL-012 on SMF progress and cumulate in the weeks following the administration of the product. All besides 1 of the 18 RZL-012-treated subjects demonstrated improvement in SMF at 84 days after treatment. On the other hand, at Day 84, none of the placebo subjects demonstrated any change in their SMF.

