#### **4.8 Submental Fat Thickness using Calipers**

The aim of caliper measurement is to evaluate fat reduction before and after treatment. At screening, caliper measurement will be made with the subject's head maintained in a neutral position. The caliper will be positioned to pinch the skin at 15 mm on either side of the center point of the submental area.

Additional measurement to assess efficacy will be conducted at study visits at Days 28, 56, and 84.

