#### **4.10 Magnetic Resonance Imaging (MRI)**

The purpose of the MRI exam is to evaluate fat reduction following treatment. MRI exams will be conducted in imaging centers close to selected clinical sites.

MRI will be conducted at screening in order to establish a baseline value for assessment of treatment efficacy. Post-treatment period MRI will be completed within 84 days ( $\pm$  14 days) after the treatment session.

Quantitative measurements such as fat volume of the SMF area will be used as an objective parameter for measurement of SMF reduction following treatment.

Sagittal 2D and 3D images of the head and neck (chin area) will be obtained using 1.5 Tesla machine (General Electric, Siemens, Phillips or other). For each MRI visit, the total imaging time is expected to be approximately thirty (30) minutes.

During the imaging, subjects will be positioned in Head first Supine recumbent. Images in the sagittal plane across the entire submental region will be collected using an appropriate MR sequence to minimize the effects of air cavities, dental implants, and amalgam on the resultant MR image. This imaging approach will generate a 2D and 3D image data set that allows for the quantification of the SMF volume in several slices covering the treatment area. In the follow up MRI exam, slices will be positioned as similar as possible to the first MRI exam.

Images should be saved in a DICOM format and include the date completed and subject's screening number to be transferred home the Sponsor's request for central analysis.

Submental volume analysis will be performed by computer-assisted tools and calculation of submental volume will be completed prior to dosing and after treatment.

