## 6. STATISTICAL ANALYSIS

- General

All measured variables and derived parameters will be listed individually and, if appropriate, tabulated by descriptive statistics.

For categorical variables, summary tables will be provided giving sample size, absolute and relative frequency and 95% CI (Confidence Interval) for proportions by study group.

For continuous variables, summary tables will be provided giving sample size, arithmetic mean, standard deviation, coefficient of variation (CV%), median, minimum and maximum and 95% CI (Confidence Interval) for means of variables by study group.

All tests will be two-tailed, and a p value of 5% or less will be considered statistically significant.

The data will be analyzed using the SAS ® version 9.4 (SAS Institute, Cary North Carolina).

Statistical methods presented in the SAP may be slightly different from those that are presented in the protocol. Differences are clearly stated and the SAP supersedes the protocol only with regard to the way data will be handled and analysed.

- Subject Disposition

A detailed description of subject accountability including count of subjects included, exposed, completed (i.e., subjects who complete the study treatment) and discontinued along with the main reason for discontinuation will be generated for each treatment group and for all subjects. All withdrawals from the study, taking place on or after study drug injection, will be fully documented in the body of the Clinical Study Report.

Demographic and Baseline Characteristics

MediStat Statistics in Medicine	DOCUMENT NUMBER: 140-BST-PLN-001	PAGE: 14 of 16
TITLE: Statistical Analysis Plan of Protocol Number RZL-012-SMF-P2bUS-001	EFFECTIVE DATE : 08/03/2022 REVISION NUMBER : 1.0	

Baseline will be defined as the last available and evaluable parameter value before and closest to the injection. If a rechecked value is used for baseline, it should be collected under the same conditions as for the planned baseline.

Baseline safety data will be presented along with subsequent safety values assessed during or after dosing.

- **Analysis of Efficacy for Primary Endpoint**

The proportion of subjects who have at least a 1-grade improvement in the C-CAT on Day 84 versus baseline will be calculated for the placebo group and the RZL-012 high-dose group along with 95% Confidence interval for proportion.

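### MRI volume and caliper thickness are each tested against placebo on two scales with neither named as the result; one log-scale ANCOVA per endpoint would give a single, slightly more precise answer

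*SAP*

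**What the plan says.** The secondary endpoints are worded without a scale. For MRI the SAP gives "Reduction in SMF volume by MRI (Day 84 versus screening) in the RZL-012 groups versus placebo group", and the caliper endpoint likewise speaks only of a reduction. Protocol 12.3 adds only this: "All other secondary endpoints will be tested using a two-sided test at the alpha=0.05 level of significance".

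The scale appears first in SAP section 6, under the analysis of secondary endpoints, and there it is doubled: "The two-sample T-test for independent samples will be applied for testing the statistical significance of the change and percentage of change from baseline". This applies to both measures and to each dose against placebo. Paired t-tests within each arm use the same two scales. SAP section 6 treats any p-value of 5% or less as significant. Neither document gives a covariate, a transformation or a rule for the case where the two scales disagree.

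A usable baseline is already planned for both measures. Protocol 4.10 says "MRI will be conducted at screening in order to establish a baseline value for assessment of treatment efficacy", and Protocol 4.8 has calipers applied at screening and says "The aim of caliper measurement is to evaluate fat reduction before and after treatment". The SAP defines the value to use: "Baseline will be defined as the last available and evaluable parameter value before and closest to the injection".

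**The concern.** With two p-values per dose and measure and no rule for choosing between them, the plan does not define what a positive MRI or caliper result is. The choice could be made after unblinding. The two tests also give two chances of a false positive per comparison, and neither adjusts for baseline. A chance difference between arms at baseline therefore carries into the estimate, and precision that the collected data could supply is left unused.

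This matters because MRI is the objective measure here and the phase 2a efficacy conclusion rested on it. Protocol 12.3 makes secondary results exploratory only if the primary analysis fails.

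**Working it through.** **The plan's own figure.** The only sample size calculation is for the primary endpoint (70% vs 35%). With pooled variance under the null, n = [1.960·√(2·0.525·0.475) + 1.282·√(0.7·0.3 + 0.35·0.65)]² / 0.35² = 40.7, so 41 per arm as stated. With 45 planned, 41/45 = 91.1%, which fits the stated dropout of about 9%. No power is stated for MRI or caliper.

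**Count of tests.** Between groups: 2 measures × 2 scales × 2 doses = 8 p-values, for 2 × 2 = 4 questions. Within groups: 2 × 2 × 3 = 12 more.

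**Inputs for size (MRI only).** Protocol 1.2.4.1.4 gives phase 2a volume changes of -22.2% ± 14.9 (high), -10.6% ± 14.5 (low) and -0.4% ± 13.9 (placebo). I read ± as SD. The documents give no baseline CV, so I assume 20%, 30% and 40%; figures in threes follow that order. They give no caliper SD, effect or correlation.

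**Two scales, no effect.** I simulated lognormal volumes with log-change SD 0.145, 45 per arm and 20,000 to 40,000 trials per setting. At least one of the change and percentage-change t-tests is significant in 5.9%, 6.2% and 6.5-6.7% of single-dose comparisons. Over both doses and both scales of one measure this is about 10.7%, 11.2% and 12%, against about 9% for one ANCOVA test per dose.

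**Precision if baseline and Day 84 SDs are equal.**
- Correlation: r = 1 - 0.145² / [2·ln(1 + CV²)] = 0.732, 0.878, 0.929.
- Variance of ANCOVA relative to a change score on the same scale: (1 + r)/2 = 0.866, 0.939, 0.965. The square roots are 0.931, 0.969 and 0.982, so the CI is about 7%, 3% and 2% narrower.
- The t-test half-width is t(88)·SD·√(2/45). The ANCOVA half-width multiplies this SD by √((1 + r)/2) and uses 3·45 - 4 = 131 df.

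| Pooled SD | t-test | ANCOVA (CV 20/30/40%) |
|---|---|---|
| 14.20 (phase 2a low vs placebo) | 5.95 | 5.51 / 5.74 / 5.82 |
| 14.41 (phase 2a high vs placebo) | 6.04 | 5.59 / 5.82 / 5.90 |

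This applies a log-scale variance ratio to an SD in percentage points, so it is an approximation.

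**Lower bound.** If percentage change is unrelated to baseline, ANCOVA and the percentage-change t-test are practically equal.

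**Imbalance.** A baseline difference of 2 SE, expected in about 5% of comparisons, moves the change-score estimate by √(2(1 - r)) = 0.73, 0.49 and 0.38 SE under equal SDs.

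**Which phase 2a group matches the current low dose.** The phase 2a low group averaged 80 mg and the high group 158.5 mg (Protocol 1.2.4.1.4), at 5 mg per site (Protocol 2.4.2). The current low dose is 163.2 ± 20.4 mg (Protocol 2.3.4) at 5.1 mg per site, so the phase 2a high group is closest. Its effect is 22.2 - 0.4 = 21.8 points with pooled SD 14.41. The t-test then has more than 99.9% power at 41 or 45 per arm. In simulation all three tests have about 100% power and the two planned tests disagree in 0.0% of trials. With log-change SD 0.19 (14.9/77.8), power is still at least about 99.8% and disagreement about 0.2% or less.

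**Sensitivity case: a smaller true effect.** With the 80 mg group's effect (10.6 - 0.4 = 10.2 points) at 45 per arm, the two planned tests disagree on significance in 3.2%, 4.8% and 7.0% of trials under equal SDs. They disagree in 2.3%, 3.9% and 5.8% if log change is unrelated to baseline. In that second case power is 93.6/93.5/93.6% for the percentage-change t-test and 93.8/93.7/93.9% for ANCOVA.

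**The case against.** The strongest reply is that the defect needs only one sentence: name percentage change as the main scale, as phase 2a reported volume, and keep the t-test. That would remove the ambiguity. If percentage change is unrelated to baseline it would also lose almost nothing in precision. It would not remove the effect of chance imbalance where regression to the mean is present, and it would give up the gain in that case. ANCOVA covers both and still reports a percent difference, so it is the better choice, but by a small margin.

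It is also fair that these are secondary endpoints in a phase 2b trial, that the excess false-positive rate is only 1 to 2 points per comparison, and that the baseline CVs are assumptions. All of that stands and limits the weight of the point.

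A reader might infer more in three ways, and the documents do not support any of them:
- That the t-tests are invalid. Randomisation makes each of them a valid test.
- That two scales nearly double the error rate. Independent tests would give 1 - 0.95² = 9.75%, but the two scales are highly correlated.
- That the low-dose comparison is short of power or likely to give conflicting verdicts. The figures that suggest this come from the phase 2a group that averaged 80 mg, about half the current low dose. The protocol does cite "supported by the dose response that shows larger effects for the higher dose of RZL", but the closer group by dose shows an effect at which the choice of test hardly matters for MRI. Because the phase 2a groups had only 8 to 10 subjects, a smaller true effect cannot be excluded, so those figures serve as a sensitivity case only.

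**Conclusion.** The point holds as a gap in prespecification with a modest statistical cost. Eight between-group p-values answer four questions, and nothing in either document says which scale is the result. With no effect, the chance that at least one scale is significant is about 6 to 6.7% per comparison. On MRI, baseline adjustment narrows the CI by about 2 to 7% under equal SDs and by about nothing, relative to percentage change, if percentage change is unrelated to baseline. These sizes rest on reading the phase 2a ± as SD and on assumed CVs of 20 to 40%. For caliper only the ambiguity can be stated. No loss of MRI power should be expected at either dose if the dose-matched phase 2a effect is near the truth. The change should be made because it is nearly free; the primary conclusion does not depend on it.

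**What to change.** Before database lock, make one ANCOVA per endpoint (MRI volume, caliper thickness) the only between-group test:
- Fit it to all three arms, with log Day 84 value as outcome and treatment and log baseline as terms, using the SAP's own baseline definition.
- Report each dose vs placebo as an adjusted ratio, expressed as a percent difference, with 95% CI and p-value. State that this is the result.
- Keep raw change, percentage change and the within-arm paired tests as descriptive.
- State which subjects enter the model, for example ITT subjects with both values. The SAP names ITT as the principal set, but its missing-data rule covers the primary endpoint only: "A subject with missing primary endpoint data will be imputed as treatment failure".

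Leave the primary chi-square test and the sample size unchanged. The cost is SAP wording and a few lines of SAS, with no new data or visits. The downside is one degree of freedom and an effect expressed as a ratio of geometric means. The change does not address multiplicity across doses and endpoints.
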